6.2 Randomization Procedures

- 6.21 The factors defined in Section 5.0, together with the registering membership, will be used as stratification factors.
- 6.22 After the patient has been registered into the study, the values of the stratification factors will be recorded, and the patient will be assigned to one of the following treatment groups using the Pocock and Simon dynamic allocation procedure which balances the marginal distributions of the stratification factors between the treatment groups (Pocock-Simon).
 - Apixaban 2.5 mg twice daily.
 - Apixaban 5 mg twice daily.

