- (1) Date and type of procedure will be recorded on the CRF;
- (2) Apixaban will be discontinued at least 48 hours prior to elective surgery or invasive procedures with a moderate or high risk of bleeding, with no drug given on the procedure date; For low bleeding risk procedures, apixaban will be discontinued at least 24 hours prior to the procedure.
- (3) Post procedure, the patient should receive appropriate DVT prophylaxis per institutional guidelines. This could include prophylactic apixaban (open label dose of 2.5 mg twice daily) dosing for 48 hours; the first prophylactic dose will be given 24 hours after the procedure. Alternatively, low molecular weight heparin or unfractionated heparin would be reasonable.
- (4) Study drug will be withheld until 48 hours after the procedure and not initiated until adequate hemostasis is confirmed.

If apixaban treatment is temporarily held for any situation, the reason will be recorded on the CRF and the patient can go back on study for up to day 365 of the treatment schedule.

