9.0 Ancillary Treatment/Supportive Care

- 9.1 Concomitant use of strong CYP3A4 inhibitors or inducers (appendix II) is prohibited.
- 9.2 Non-steroid anti-inflammatory drugs (NSAIDs) and antiplatelet agents (aspirin) are discouraged but not prohibited. If aspirin use is required, then the dose should be ≤ 100 mg daily. The use of these drugs should be recorded on the CRF.
- 9.3 **Note:** Antiplatelet therapy with a thienopyridine (clopidogrel, prasugrel, or ticagrelor) is an exclusion criterion and not allowed while on protocol therapy.
- 9.4 Measures necessary for minor and major bleeds should be utilized.
- 9.5 Other anticoagulants should not be used concomitantly (aside from those noted in Section 8.2).

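### After a procedure, the stated windows for open-label prophylactic apixaban and for study drug can overlap by up to 24 hours, and Section 8.2 does not say whether the two may be taken together

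*Combined protocol and SAP*

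**What the plan says.** All references are to the combined protocol and SAP.

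- **Section 8.2, item (3).** Some prophylaxis is expected: "Post procedure, the patient should receive appropriate DVT prophylaxis per institutional guidelines". One permitted form is open-label apixaban at 2.5 mg twice a day, with this timing: "dosing for 48 hours; the first prophylactic dose will be given 24 hours after the procedure". Heparin is the other: "Alternatively, low molecular weight heparin or unfractionated heparin would be reasonable". No duration is given for the heparin option.
- **Section 8.2, item (4).** "Study drug will be withheld until 48 hours after the procedure and not initiated until adequate hemostasis is confirmed". This sets an earliest time and adds a clinical condition. It does not set a fixed restart time.
- **Section 6.2.** The randomised regimens are "Apixaban 2.5 mg twice daily" and "Apixaban 5 mg twice daily".
- **Section 9.5.** "Other anticoagulants should not be used concomitantly (aside from those noted in Section 8.2").
- **Section 15.17.** The drug-information text lists apixaban with other anticoagulants as a combination to avoid.

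No section says that open-label apixaban ends when study drug restarts, or that study drug waits until the open-label course is complete.

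**The concern.** Items (3) and (4) each give a time measured from the procedure, but the two times do not meet. The open-label course, taken at its stated length, is still running at the earliest hour at which study drug is allowed back. A site that follows each item literally can have a patient on two apixaban supplies at once. Treatment is blinded, so the clinician would not know which total dose the patient was taking.

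The general rule that might catch this, Section 9.5, carves out the agents named in Section 8.2. Section 15.17 points the other way but sits in the drug-information section and does not mention the post-procedure pathway. Site staff are left to decide which text governs.

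What is at stake is mainly the individual patient in the days after a procedure, a period that item (4) itself treats as bleeding-sensitive by making restart depend on hemostasis. There is a secondary interest for the analysis. The trial compares bleeding between two apixaban doses, and a patient taking both supplies is for that time on neither randomised regimen.

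**Working it through.** The plan gives no overlap figure to reproduce. The check is a timeline and a sum of doses.

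**Inputs**
- Open-label dose 2.5 mg twice daily, first dose at hour 24, duration 48 hours: Section 8.2(3).
- Earliest restart of study drug at hour 48, conditional on hemostasis: Section 8.2(4).
- Study dose 2.5 mg or 5 mg twice daily: Section 6.2.
- Assumption: twice daily means every 12 hours.

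**Step 1: open-label window.** End = first dose + duration = 24 + 48 = hour 72. Doses fall at hours 24, 36, 48 and 60.

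**Step 2: overlap.** Overlap = max(0, 72 − restart hour).

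| Study drug restarts at hour | Overlap (hours) | Open-label doses at or after restart |
|---|---|---|
| 48 | 72 − 48 = 24 | 2 (hours 48 and 60) |
| 60 | 72 − 60 = 12 | 1 (hour 60) |
| 72 | 0 | 0 |
| 84 | 0 | 0 |

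**Step 3: alternative reading of the duration.** If the 48 hours are counted from the procedure, open-label dosing runs from hour 24 to hour 48, with doses at 24 and 36, and the overlap is 0. That leaves 48 − 24 = 24 hours of dosing, which does not fit the stated 48-hour duration.

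**Step 4: daily apixaban during an overlap.** Total = 2 × (study dose + 2.5 mg).
- 2.5 mg arm: 2 × (2.5 + 2.5) = 10 mg, against 2 × 2.5 = 5 mg alone (10/5 = 2.0-fold).
- 5 mg arm: 2 × (5 + 2.5) = 15 mg, against 2 × 5 = 10 mg alone (15/10 = 1.5-fold).

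**Step 5: scale within the treatment period.** The maximum is 1 day per procedure out of 365 treatment days: 1/365 = 0.27%, about 0.3%. The documents give no procedure rate, so this cannot be turned into an expected number of affected patients or bleeds.

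**Heparin option.** It has no stated stop time, so whether it may continue past the restart of study drug is equally open. No overlap length can be calculated for it.

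**The case against.** The strongest reply is that the two items do not contradict each other. Hour 48 is a floor with a hemostasis condition attached. A patient who completes the open-label course at hour 72 and then resumes study drug complies with both items in full. Prophylaxis is also naturally read as cover for the time when study drug is withheld, which suggests substitution rather than addition. Open-label apixaban is only one choice among several, left to institutional guidelines. Section 15.17, and the nursing guidance in Section 15.19b on avoiding other agents with the study medication, both weigh against taking two supplies together. The exemption in Section 9.5 has an ordinary purpose: to allow the bridging agents that Section 8.2 lists.

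All of this stands, and it rules out some readings that a reader might infer:

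- **That the protocol directs patients to take both supplies.** It does not. It permits this by leaving the sequence unstated.
- **That nothing in the protocol speaks against combining them.** Sections 15.17 and 15.19b do, in general terms, although neither names open-label apixaban.
- **That the overlap falls when bleeding risk is at its peak.** Any overlap starts no earlier than hour 48 and only after hemostasis is confirmed, and the documents give no bleeding risk by hour.
- **That the case report form fails to capture the dates and times.** Concomitant-medication and dose-omission forms are listed in Section 18.1, but their fields are not shown, so this cannot be judged.

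What the reply does not remove is the gap itself. A sequential reading is available, but no sentence requires it, and a restart at hour 48 during the open-label course also complies with items (3) and (4) and Section 9.5 as written.

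**Conclusion.** The point holds in limited form. On the literal reading, Section 8.2 allows open-label and study apixaban to run together for up to 24 hours after a procedure, with daily totals of up to 10 mg and 15 mg in the two arms. The size rests on three conditions: the open-label apixaban option is chosen, its 48 hours are counted from the first dose, and study drug restarts before hour 72. If any one fails, there is no overlap of the two apixaban supplies.

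A reader might go further and infer that the overlap biases the primary bleeding comparison, since the relative increase is larger in the 2.5 mg arm. The documents do not support that. They give no procedure rate and no bleeding rate for the window. The attribution issue is also not specific to overlap: Section 16.21 counts bleeds during treatment or within 7 days of discontinuation, so a bleed on a strictly sequential open-label bridge could also be counted to the randomised arm. The effect on the primary endpoint is unquantified and probably small.

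This is therefore a patient-safety inconsistency in one optional pathway. It is worth correcting because the correction is easy. It is not a demonstrated bias and does not call the design or analysis into question.

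**What to change.** Add one sentence to Section 8.2 stating whether open-label prophylaxis, apixaban or heparin, and study drug may be taken in the same period. Make items (3) and (4), Section 9.5 and Section 15.17 agree with it. Which sequence, timing and dose apply is a clinical decision for the sponsor, and none is proposed here.

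At the same time, check that the existing forms record when post-procedure prophylaxis starts and stops and when study drug restarts. If they already do, nothing needs adding.

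The cost is a wording clarification, with at most two time fields on the case report form. Sample size and analysis are unaffected.

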9.0 Ancillary Treatment/Supportive Care

- 9.1 Concomitant use of strong CYP3A4 inhibitors or inducers (appendix II) is prohibited.
- 9.2 Non-steroid anti-inflammatory drugs (NSAIDs) and antiplatelet agents (aspirin) are discouraged but not prohibited. If aspirin use is required, then the dose should be ≤ 100 mg daily. The use of these drugs should be recorded on the CRF.
- 9.3 **Note:** Antiplatelet therapy with a thienopyridine (clopidogrel, prasugrel, or ticagrelor) is an exclusion criterion and not allowed while on protocol therapy.
- 9.4 Measures necessary for minor and major bleeds should be utilized.
- 9.5 Other anticoagulants should not be used concomitantly (aside from those noted in Section 8.2).

10.0 Adverse Event (AE) Reporting and Monitoring

10.1 Adverse Event Characteristics

An Adverse Event [AE] is defined as any new untoward medical occurrence or worsening of a preexisting medical condition in a patient or clinical investigation subject administered an investigational (medicinal) product and that does not necessarily have a causal relationship with this treatment. An AE can therefore be any unfavorable and unintended sign (including an abnormal laboratory finding, for example), symptom, or disease temporally associated with the use of investigational product, whether or not considered related to the investigational product.

CTCAE term (AE description) and grade: The descriptions and grading scales found in the revised NCI Common Terminology Criteria for Adverse Events (CTCAE) version 4.0 will be utilized for AE reporting. All appropriate treatment areas should have access to a copy of the CTCAE version 4.0. A copy of the CTCAE version 4.0 can be downloaded from the CTEP web site:

10.11 Adverse event monitoring and reporting is a routine part of every clinical trial. First, identify and grade the severity of the event using the CTCAE version 4.0. Next, determine whether the event is expected or unexpected (see Section 10.2) and if the adverse event is related to the medical treatment or procedure (see Section 10.3). With this information, determine whether the event must be reported as an expedited report (see Section 10.4). **Important:** Expedited adverse event reporting requires submission of a Med Watch 3500A report(s). Expedited reports are to be completed within the timeframes and via the mechanisms specified in Sections 10.4. All AEs reported via expedited mechanisms must also be reported via the routine data reporting mechanisms defined by the protocol (see Sections 10.5 and 18.0).

10.12 Each CTCAE term in the current version is a unique representation of a specific event used for medical documentation and scientific analysis and is a single MedDRA Lowest Level Term (LLT).

- **NOTE:** A severe AE, as defined by the above grading scale, is **NOT** the same as serious AE which is defined in the table in Section 10.4.

10.2 Expected vs. Unexpected Events

- The determination of whether an AE is expected is based on agent-specific information provided in Section 15.0 of the protocol.
- Unexpected AEs are those not listed in the agent-specific information provided in Section 15.0 of the protocol (determined based on Reference Safety Information from the current investigator brochure for Apixaban).

NOTE: “Unexpected adverse experiences” means any adverse experience that is neither identified in nature, severity, or frequency of risk in the information provided for IRB review nor mentioned in the consent form.

10.3 Assessment of Attribution

When assessing whether an adverse event is related to a medical treatment or procedure, the following attribution categories are utilized:

- Definite - The adverse event is *clearly related* to the agent(s).
- Probable - The adverse event is *likely related* to the agent(s).
- Possible - The adverse event *may be related* to the agent(s).
- Unlikely - The adverse event is *doubtfully related* to the agent(s).
- Unrelated - The adverse event is *clearly NOT related* to the agent(s).

Events determined to be possibly, probably or definitely attributed to a medical treatment suggest there is evidence to indicate a causal relationship between the drug and the adverse event.

10.31 Special Situations for Expedited Reporting

10.311 Persistent or Significant Disabilities/Incapacities

Any AE that results in persistent or significant incapacity or substantial disruption of the ability to conduct normal life functions (formerly referred to as disabilities), congenital abnormalities or birth defects, must be reported immediately if they occur at any time following treatment with an agent under an IND/IDE since they are considered to be a serious AE and must be reported to the sponsor as specified in 21 CFR 312.64(b).

10.312 Death

- Any death occurring within 30 days of the last dose, regardless of attribution to an agent/intervention under an IND/IDE requires expedited reporting within 24-hours.
- Any death occurring greater than 30 days with an attribution of possible, probable, or definite to an agent/intervention under an NCI IND/IDE requires expedited reporting within 24-hours.
- **Reportable categories of Death**
 - Death attributable to a CTCAE term.
 - Death Neonatal: A disorder characterized by cessation of life during the first 28 days of life.
 - Death NOS: A cessation of life that cannot be attributed to a CTCAE term associated with Grade 5.
 - Sudden death NOS: A sudden (defined as instant or within one hour of the onset of symptoms) or an unobserved cessation of life that cannot be attributed to a CTCAE term associated with Grade 5.
 - Death due to progressive disease should be reported as **Grade 5 “Neoplasms benign, malignant and unspecified (incl cysts and polyps) – Other (Progressive Disease)”** under the system organ class (SOC) of the same name. Evidence that the death was a manifestation of underlying disease (e.g., radiological changes suggesting tumor growth or progression: clinical deterioration associated with a disease process) should be submitted.

10.313 Secondary Malignancy

- A **secondary malignancy** is a cancer caused by treatment for a previous malignancy (e.g., treatment with investigational agent/intervention, radiation or chemotherapy). A secondary malignancy is not considered a metastasis of the initial neoplasm.
- All secondary malignancies that occur following treatment with an agent under an IND/IDE to be reported. Three options are available to describe the event:
 - Leukemia secondary to oncology chemotherapy (e.g., Acute Myelocytic Leukemia [AML])
 - Myelodysplastic syndrome (MDS)
 - Treatment-related secondary malignancy
- Any malignancy possibly related to cancer treatment (including AML/MDS) should also be reported via the routine reporting mechanisms outlined in each protocol.

10.314 Second Malignancy

- A second malignancy is one unrelated to the treatment of a prior malignancy (and is NOT a metastasis from the initial malignancy). Second malignancies require ONLY routine reporting.

10.315 Pregnancy

If, following initiation of the investigational product, it is subsequently discovered that a study subject is pregnant or may have been pregnant at the time of investigational product exposure, including during at least 5 half-lives after product administration, the investigational product will be permanently discontinued in an appropriate manner (eg, dose tapering if necessary for subject safety).

The site investigator must immediately notify ACCRU of this event via the Pregnancy Surveillance Form (found in the forms packet) within 24 hours and in accordance with SAE reporting procedures in Section 10.4.

Follow-up information regarding the course of the pregnancy, including perinatal and neonatal outcome and, where applicable, offspring information must be reported on a Pregnancy Surveillance Form.

Any pregnancy that occurs in a female partner of a male study participant should be reported to BMS. Information on this pregnancy may also be collected on the Pregnancy Surveillance Form.

Protocol-required procedures for study discontinuation and follow-up must be performed on the subject unless contraindicated by pregnancy

(eg, x-ray studies). Other appropriate pregnancy follow-up procedures should be considered if indicated.

10.316 Overdose

An overdose is defined as the accidental or intentional administration of any dose of a product that is considered both excessive and medically important. All occurrences of overdose must be reported as SAEs.

10.317 Adverse Events of Special Interest

In this study, the following adverse events are to be reported to BMS, regardless of whether these reports are classified as serious or unexpected:

- Potential or suspected cases of liver injury including but not limited to liver test abnormalities, jaundice, hepatitis or cholestasis.
(NOTE: If liver toxicity becomes clinically apparent, it must be evaluated and then reported.)

Adverse drug reactions (related SAEs) should be reported. If hepatic failure, clearly occur due to the meta or primary malignancy, it should not be considered related, therefore not reportable to BMS.

10.318 Other Safety Considerations

Any significant worsening noted during interim or final physical examinations, electrocardiograms, x-rays, and any other potential safety assessments, whether or not these procedures are required by the protocol, should also be recorded as a nonserious or serious adverse event, as appropriate, and reported accordingly.

10.4 Expedited Reporting Requirements for Studies using Commercial Agent(s) ONLY:

Expedited Reporting Requirements for Adverse Events that Occur in a Non-IND/IDE trial within 30 Days of the Last Administration of a Commercial Agent^{1,2}

FDA REPORTING REQUIREMENTS FOR SERIOUS ADVERSE EVENTS (21 CFR Part 312)

NOTE: Investigators **MUST** immediately report to ACCRU **ANY** Serious Adverse Events, whether or not they are considered related to the investigational agent(s)/intervention (21 CFR 312.64)

An adverse event is considered serious if it results in **ANY** of the following outcomes:

- 1) Death
- 2) A life-threatening adverse event
- 3) An adverse event that results in inpatient hospitalization or prolongation of existing hospitalization for ≥ 24 hours
- 4) A persistent or significant incapacity or substantial disruption of the ability to conduct normal life functions
- 5) A congenital anomaly/birth defect.
- 6) Important Medical Events (IME) that may not result in death, be life threatening, or require hospitalization may be considered serious when, based upon medical judgment, they may jeopardize the patient or subject and may require medical or surgical intervention to prevent one of the outcomes listed in this definition. (FDA, 21 CFR 312.32; ICH E2A and ICH E6).

ALL SERIOUS adverse events that meet the above criteria **MUST** be immediately reported to ACCRU within the timeframes detailed in the table below.

| Hospitalization | Grade 1 Timeframes | Grade 2 Timeframes | Grade 3 Timeframes | Grade 4 & 5 Timeframes |
|--|--------------------|--------------------|--------------------|---------------------------|
| Resulting in Hospitalization ≥ 24 hrs | | 1 Business Day | | 24-hour 1 Business Day |
| Not resulting in Hospitalization ≥ 24 hrs | Not required | | 1 Business Day | |

Expedited AE reporting timelines are defined as:

- “24-Hour; 1 Business Day” - The AE must initially be reported via MedWatch within 24 hours of learning of the AE, followed by a complete expedited report within 1 business day of the initial 24-hour report.
- “1 Business Day” - A complete expedited report on the AE must be submitted within 1 business day of learning of the AE.

¹Serious adverse events that occur more than 30 days after the last administration of investigational agent/intervention and have an attribution of possible, probable, or definite require reporting as follows:

Expedited 24-hour notification followed by complete report within 1 business day for:

- All Grade 4, and Grade 5 AEs

Expedited 1 business day reports for:

- Grade 2 adverse events resulting in hospitalization or prolongation of hospitalization
- Grade 3 adverse events

² For studies using PET or SPECT IND agents, the AE reporting period is limited to 10 radioactive half-lives, rounded UP to the nearest whole day, after the agent/intervention was last administered. Footnote “1” above applies after this reporting period.

Effective Date: May 5, 2011

Additional Instructions:

1. An increased incidence of an expected adverse event (AE) is based on the patients treated for this study at their site. A list of known/expected AEs is reported in the package insert or the literature, including AEs resulting from a drug overdose.
2. Follow site-specific reporting guidelines.
3. Submit form 3500A to the FDA, MedWatch, [REDACTED]
[REDACTED]
4. Submit copies to the ACCRU SAE Coordinator via fax [REDACTED] The ACCRU SAE Coordinator will forward the report to Bristol-Myers Squibb via E-mail within 1 business day to [REDACTED]

If only limited information is initially available, follow-up reports are required. (Note: Follow-up SAE reports should include the same investigator term(s) initially reported.) If an ongoing SAE changes in its intensity or relationship to study drug or if new information becomes available, a follow-up SAE report should be sent within 24 hours to the BMS (or designee) using the same procedure used for transmitting the initial SAE report.

All SAEs should be followed to resolution or stabilization.

5. The ACCRU SAE Coordinator will forward to [REDACTED] as appropriate. The ACCRU IND Coordinator will assist the sponsor-investigator in notifying the FDA if required.

